- (3) The weight loss-induced changes in serum ex-vivo bioassay results and serum IGF-1 & IGFBP-1 levels will directly correlate with the proliferative, apoptotic, and IGF axis changes seen in prostate cancer tissue. Specifically, we expect that: (a) Increased weight loss will correlate with a fall in serum IGF-I and a rise in serum IGFBP-1 as well as with a reduction in the ex-vivo proliferation bioassay and increase in ex-vivo apoptosis bioassay. (b) Increased weight loss will correlate with increased apoptosis staining and decreased Ki67 staining in the prostate cancer tissue. (c) The post-intervention change in the serum ex-vivo proliferation and apoptosis bioassays and serum IGF-I and IGFBP-1 levels will directly

correlate with the change in tissue proliferation and apoptosis making these markers clinical tools for secondary prevention prostate cancer weight loss trials.

Objective 1. To evaluate if weight loss prior to radical prostatectomy in overweight and obese men results in antiproliferative and pro-apoptotic effects on prostate cancer tissue histopathology. Overweight and obese men that have elected to undergo radical prostatectomy will be randomized to a control group (no weight loss) vs. a 4-9-week weight loss program followed by radical prostatectomy. Proliferation (Ki67) and apoptosis (TUNEL) of the prostate cancer tissue will be compared between the groups. We will also compare the proliferation and apoptosis indices between the baseline prostate needle biopsy specimens and corresponding radical prostatectomy specimens. In addition, prostate cancer tissue IGF-axis RNA and protein levels (IGF-1, total and phospho-IGF-1 receptor, and down-stream molecules), will be compared between the weight loss and control groups.

Objective 2. To evaluate if weight loss prior to radical prostatectomy in overweight and obese men impacts on the circulating levels of IGF-related analytes and on the Ex-vivo mitogenic and apoptotic activity of patient sera on LNCaP cell lines. The ex-vivo mitogenic and apoptosis bioassay in LNCaP cells will be performed on pre and post sera from the Control Group – No Weight Loss and Weight Loss Group at baseline and prior to radical prostatectomy. In addition we will compare baseline and post-intervention serum IGF-I and IGFBP-1 levels by ELISA.

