Immunostaining and Interpretation: Immunostaining of paraffin embedded pretreatment prostate needle biopsy specimens and malignant tissue from radical prostatectomy specimens will be performed using ki67 monoclonal antibodies (DAKO) and a TUNEL assay (BioVision). The cancer tissue with the highest Gleason grade will be analyzed in a blinded fashion by counting 300 cancer cells per slide. Our main objective (Objective 1 of this proposal) will be to compare the percent of cells staining positive for ki67 and TUNEL between the Control Group-No Weight Loss and Weight Loss Group (controlling for Gleason grade). We will also compare the percent of cells staining for ki67 and TUNEL in the prostate needle biopsy specimen relative to the prostatectomy tissue (also matching for Gleason grade). In addition, we will perform correlation analysis to determine if weight loss correlates with proliferation and apoptosis. We hypothesize that with increasing weight loss there will be decreased ki67 staining and an increasing percentage of cells with TUNEL staining. To further evaluate the effect of weight-loss on prostate tumor staining of the IGF signaling cascade we will analyze immunostaining of phospho-IGF-1R (using a Cell Signaling antibody) and phospho-Akt (Cell Signaling). We will also evaluate for earlier stages of apoptosis as measured by activated caspase-3 (Oncogene). If we detect changes in apoptosis, we will also stain for BAX and BCL2 using antibodies from R&D. If we detect changes in proliferation as measured by ki67 staining, we will also stain for Mcm-2 (which has been shown to be a prognostically important prostate cancer proliferation marker) using antibodies from R&D.⁶⁶

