Statistical Design: The statistical design of this study is a randomized repeated measures utilizing random mixed block sizes known only to the statistician constructing the randomization list to assign subjects to two study arms in a ratio of 7:6, weight loss to no weight loss.

Sample Size Determination: An evaluable sample of at least 60 subjects (no weight loss=30, weight loss=30) is expected to provide 80% power to detect an effect size of 0.74 using a two group t-test with a 0.050 two-sided significance when comparing the apoptotic index (primary outcome variable) in the radical prostatectomy malignant epithelium between the weight loss and no Weight Loss Group. The apoptotic index will be measured in the malignant epithelium with the highest Gleason grade. To account for a post-randomization attrition rate of up to 15% in the Weight Loss Group, a total of 35 subjects will be randomized to the Weight Loss Group, thus bringing the total sample size to 65 subjects. Kim et al. observed an effect size of 1.74 on apoptotic index using a nutritional intervention in a similar study.⁶⁴

Data Analysis: Data analyses will be performed on randomized subjects who complete the study. All parameters measured will be summarized descriptively. The number of subjects, mean, standard error of the mean, median and min-max values will be presented for continuous parameters and the number and percentage of subjects in each category will be presented for categorical parameters. No imputation of missing data is planned. Demographic and baseline characteristics will be summarized using descriptive statistics overall and by treatment group to assess baseline comparability. Treatment groups will be compared using the appropriate nonparametric tests for categorical parameters and analysis of variance models for continuous parameters.

Primary Outcome Variable: The primary outcome variable is apoptotic index of the highest Gleason grade malignant epithelium in the radical prostatectomy specimen. The primary objective is to compare the mean apoptotic index between the Weight Loss Group and the Control Group-No Weight Loss. The two independent sample t-test will be used to compare the index between the groups. If the index is non-normally distributed we will use the Wilcoxon rank sum test. Next, linear regression models will be constructed to test whether the treatment effect

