is significant after controlling for Gleason grade, stage and any demographic factors that are significantly different between the groups.

Secondary Outcome Variables: The secondary outcome variables are: the proliferative index in prostate cancer epithelium obtained from the radical prostatectomy specimen, the change in apoptotic and proliferative indices of malignant epithelium between the diagnostic prostate needle biopsy and corresponding radical prostatectomy, the change (baseline vs post-intervention) in serum IGF-related analytes: IGF-1 and IGFBP-1, the ex-vivo mitogenic and apoptotic activity of patient sera on LNCaP cells, and the change in body weight and percent body fat by DEXA over 4-9-weeks.

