Secondary Statistical Analyses: The statistical methods for these analyses will be analysis of variance (ANOVA), linear regression, and correlation analysis. ANOVA will be used to determine if the serum biomarkers (IGF-I, IGFBP-1, proliferation and apoptosis bioassays) change over the course of time. These models will include a term for time, treatment (weight-loss versus no weight loss) and the time by treatment interaction effect. We will also construct ANOVA models for weight and body fat over time to determine if the treatment by time effect (intervention effect) is significant. Next, linear regression models will be constructed for each biomarker to assess the factors that predict change in that marker. Predictors will include actual weight loss (percent change), group, grade, PSA, percent body fat, and demographic factors. These models will allow us to assess the direct effect of weight loss on each of the serum biomarkers and allow for the assessment of whether weight change or intervention is the primary factor predicting change in the biomarkers. This assessment is required due to the fact that the intervention will have varying effects on weight based on the amount of subject compliance with the weight loss regime. Regression models will also be constructed to compare the groups with respect to the pre-prostatectomy biomarkers and the tissue markers and the between group tissue markers (apoptosis, Ki67 staining). A separate model will be constructed for each marker including the predictors of group, grade, PSA, percent body fat and demographic factors. Next, we will construct regression models to determine if the biomarkers, or change in biomarkers, affect the post-op pathology. Ordinal regression will be used for post-op pathology. These models will include terms for the demographic factors and for each of the biomarkers. Since there are a large number of biomarkers we will first construct single biomarker models which will include the covariates for each outcome and then combine together all significant markers into multiple regression models. Finally, we will use the Spearman correlation to test for correlations between pre-prostatectomy biomarkers and the tissue markers. This analysis will specifically address **Objective 3** of the proposal, that being to determine if a correlation exists between serum biomarkers and tissue biomarkers. The Spearman correlation is a non-parametric rank based correlation measure that does not depend on the assumption that the markers are normally distributed.

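### The biopsy-to-prostatectomy change in TUNEL and Ki67 is a secondary outcome without an assigned between-arm test, so a shift common to both arms could be read as an effect of weight loss

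*Combined protocol and SAP*

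**What the plan says.** Objective 1 (section 1, Rationale) first sets out a comparison between the randomized groups and then adds: "We will also compare the proliferation and apoptosis indices between the baseline prostate needle biopsy specimens and corresponding radical prostatectomy specimens". The arms are not mentioned in that sentence.

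Immunostaining and Interpretation (section 3) has the same structure. It states the main comparison of Ki67 and TUNEL between the two groups, and the next sentence reads: "We will also compare the percent of cells staining for ki67 and TUNEL in the prostate needle biopsy specimen relative to the prostatectomy tissue". A parenthesis adds matching for Gleason grade. Again only specimens are named.

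Secondary Outcome Variables lists "the change in apoptotic and proliferative indices of malignant epithelium between the diagnostic prostate needle biopsy and corresponding radical prostatectomy" and attaches no test.

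Secondary Statistical Analyses says "ANOVA will be used to determine if the serum biomarkers (IGF-I, IGFBP-1, proliferation and apoptosis bioassays) change over the course of time", and those models carry a time-by-treatment interaction. Weight and body fat also get a treatment-by-time test. The tissue indices appear in neither model. They have a separate regression with group as a predictor, but its outcome is the marker itself rather than its change, and the biopsy index is not among the listed predictors.

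**The concern.** A needle core and a surgical specimen differ in how they are obtained and sampled, and time passes between them. Either could move TUNEL or Ki67 in every man, whichever arm he is in. A contrast of biopsy with prostatectomy tissue mixes that shift with any effect of the intervention, and only the control arm can separate them. The plan collects control-arm tissue but does not say that it will be used for this outcome.

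The result has consequences. Immunostaining and Interpretation makes further staining (BAX and BCL2, or Mcm-2) depend on detecting a change in apoptosis or proliferation, without saying which comparison decides. The Significance paragraph would start larger trials on evidence of more apoptosis or less proliferation.

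**Working it through.** **Inputs from Sample Size Determination**
- "An evaluable sample of at least 60 subjects (no weight loss=30, weight loss=30").
- "80% power to detect an effect size of 0.74 using a two group t-test with a 0.050 two-sided significance", for the primary outcome only. No power figure is given for the tissue change.

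**Assumptions, because the documents give no value**
- A specimen or time shift that is equal in both arms, of 0.3, 0.5 or 0.7 SD of the within-man change.
- A biopsy-prostatectomy correlation ρ from 0 to 0.75, with equal SDs for the two specimens.

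**Step 1. The plan's own figure.** Noncentral t with 58 degrees of freedom: noncentrality = 0.74 × √(30/2) = 2.87, critical value 2.00, power 80.5%. The stated 80% reproduces.

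**Step 2. Error if the change is judged within arms.** Suppose there is no intervention effect. For a shift of d SD, a paired t-test on 30 men has noncentrality d√30, 29 degrees of freedom and critical value 2.05. If p is the chance of significance in one arm, the chance that the weight-loss arm alone is significant is p(1−p), because the arms are independent.

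| Shift d | Noncentrality | p | Weight-loss arm only, p(1−p) | Between-arm test of change |
|---|---|---|---|---|
| 0.3 | 1.64 | 36% | 0.355 × 0.645 = 23% | 5% |
| 0.5 | 2.74 | 75% | 0.754 × 0.246 = 19% | 5% |
| 0.7 | 3.83 | 96% | 0.959 × 0.041 = 4% | 5% |

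With both arms pooled (60 men), the before-after test is significant in 63% of trials at 0.3 SD and 97% at 0.5 SD.

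The last column is 5% by construction, because a common shift cancels in the difference between arms. Simulation (20,000 trials per setting; shifts of 0.25 to 0.74 SD of the index itself; ρ of 0 and 0.5) gave 4.7% to 5.2% for the between-arm test and 2% to 25% for the weight-loss-only pattern.

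**Step 3. Which between-arm test.** With 30 per arm and a true effect of 0.74 SD of the index, the SD of a change score is √(2(1−ρ)) times the index SD. The residual SD under ANCOVA is √(1−ρ²) times the index SD. Dividing 0.74 by each factor and repeating step 1:

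| ρ | 0.74/√(2(1−ρ)) | Power, change score | 0.74/√(1−ρ²) | Power, ANCOVA |
|---|---|---|---|---|
| 0 | 0.52 | 51% | 0.74 | 80% |
| 0.25 | 0.60 | 63% | 0.76 | 83% |
| 0.5 | 0.74 | 80% | 0.85 | 90% |
| 0.75 | 1.05 | 98% | 1.12 | 99% |

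The degree of freedom that ANCOVA spends on the biopsy index changes none of these rounded figures.

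**The case against.** **The plan is silent; it does not choose a wrong test.** No section names a paired, arm-by-arm or pooled before-after test for this outcome. A reader might infer that the plan commits to one, and the documents do not support that. The rates in step 2 belong to tests that a literal reading invites, not to tests that the plan prescribes. This stands.

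**Some text leaves room for a between-arm test.** Statistical Design calls the trial a randomized repeated-measures design. Data Analysis says that treatment groups will be compared by analysis of variance for continuous parameters. Secondary Statistical Analyses describes regressions for the change in each biomarker, with group as a predictor. But the analysis-of-variance sentence directly follows the one on baseline comparability, and the text after the regression predictors speaks of serum biomarkers. These passages permit the right test without assigning it to the tissue change.

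**Gleason matching protects the comparison.** It does so in part, since it deals with differences in grade. It does not remove other differences between core and surgical tissue, or the effect of time.

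**The randomized comparisons stand beside it.** This is correct and limits the point. The primary t-test and the tissue regressions compare arms on prostatectomy tissue, where a common shift cancels. A reader might infer that the trial's main result is exposed; it is not.

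**The error rates could be put higher.** Significance in exactly one arm would occur in 46% of trials at 0.3 SD and 37% at 0.5 SD. Half of those trials are significant in the control arm alone and could not be credited to weight loss, so 23% and 19% are the relevant figures.

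**Conclusion.** The concern holds for this one secondary outcome. The plan defines the tissue change as specimen against specimen and assigns it no between-arm test, while it assigns one to the change in serum markers, weight and body fat. What is shown is a risk of misreading and not a demonstrated bias: the documents contain no evidence that a specimen or time shift exists, or that it would run in the direction favourable to weight loss. Under an assumed common shift of 0.3 to 0.5 SD of the within-man change and no intervention effect, a paired test on 30 men would be significant in 36% to 75% of trials, and in the weight-loss arm alone in about 19% to 23%, against 5% for a between-arm test. At 0.7 SD the weight-loss-only pattern falls to about 4%, because both arms are then usually significant. The change is worth making because it costs little and uses tissue that is already planned.

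**What to change.** In Immunostaining and Interpretation, Secondary Outcome Variables and Secondary Statistical Analyses, state that:
- the tissue-change outcome is tested between arms, for TUNEL and Ki67 separately;
- the model is an ANCOVA of the prostatectomy index on arm, biopsy index and Gleason grade, or else a time-by-treatment term as for the serum markers;
- the between-arm difference is reported with a 95% confidence interval;
- within-arm changes from biopsy to prostatectomy are descriptive and support no claim about the intervention.

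ANCOVA is preferable to change scores on the power shown in step 3 (80% to 99% against 51% to 98%).

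The cost is wording. Staining of biopsy and prostatectomy tissue is not restricted to one arm, and the sample size does not change. The small downside is that men without evaluable tumour in the biopsy drop out of this secondary analysis; their number per arm should be reported.

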3. WORK PROPOSED

Overview: The study design for the present proposal is illustrated below. To obtain adequate power to detect a difference in prostate tumor apoptosis between the groups, the trial will require 30 patients per group. Based on our prior experience with the weight loss intervention we will be using in this trial, we are assuming a 15% dropout rate in the Weight Loss Group. Therefore, we are adding an additional 5 subjects to the Weight Loss Group to bring the total in this group to 35 and the total in the overall trial to 65.

Screening and Recruitment of Subjects - Minority Participation: Subjects will be recruited for the present trial from the VA Medical Center, Greater Los Angeles Health Care System. [name] conducts the urologic oncology clinic at the VA in which 130 new prostate cancer cases are diagnosed per year. Subjects with a new diagnosis of prostate cancer at the VA are offered standard therapies as well as the opportunity to participate in clinical trials. Subjects expressing interest in the weight loss trial will be given the consent form to review and the phone number of [name] research coordinator. Given the high prevalence of overweight and obese subjects (up to 70 % at our VA¹⁰), and given the high number of radical prostatectomy procedures performed at our VA (40/year), we anticipate no problem meeting our

recruitment goal of 65 subjects over 5-years. As well, given that 40-50% of men that undergo radical prostatectomy at the VA are AAM, we anticipate 40-50% of men in our clinical trials will be AAM.⁶² This is extremely important given the increased risk of obesity in AAM and the undue burden of increased morbidity and mortality of prostate cancer in AAM. For men randomized to the weight loss intervention group, the 4-9 week delay in radical prostatectomy has been shown not to increase the risk of biochemical recurrence.⁶³ However, we will not enter patients in this trial with a high risk of having advanced disease (Gleason Grade > 4+4) to avoid the potential risk (albeit extremely low) for progression during the weight loss intervention.

Inclusion Criteria:

1. Subject is overweight or obese (BMI > 25 kg/m²)
2. Patient with pathologically confirmed adenocarcinoma of the prostate and has elected to undergo radical prostatectomy
3. Able to adhere to physical activity intervention (able to walk for 10 minutes without rest)

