Control – No Weight Loss Intervention Group: After randomization to the control group, these men will proceed with radical prostatectomy as scheduled. They will have one additional visit to the VA CRC within 3 days prior to radical prostatectomy for measurement of weight, height, and waist to hip ratio, fasting blood will be collected for biomarkers and a DEXA Scan. During the week prior to the radical prostatectomy a 3-Day Food Record will be completed as well. We are doing this second visit in the control group to monitor for possible weight loss that these subjects may initiate on their own, although we do not anticipate this occurring to any significant degree. Subjects in the Control group will be given the phone number of the study coordinator to schedule their optional 5-8-week weight loss program after they have recovered from their surgery. This optional weight loss program is given as an incentive for their participation in the trial.

Weight Loss Intervention Group: Subjects randomized to the Weight Loss Group will receive an appointment to the VA CRC to meet with the research study coordinator and the study dietician to initiate the weight loss intervention. Subjects will receive one of two standard structured energy-restricted meal plans (1200, 1500, 1800 Kcal/day) using meal replacements and portion-controlled foods. Prescribed plans will be based upon resting energy expenditure and lean body mass as determined by DEXA scanning. The goal of the meal plan is to provide a total calorie intake incorporating 500-800 Calorie deficits per day. Since men will be provided with exercise regimens as well, they should experience a 1 to 2 pound weight loss per week during the weight loss intervention. Based on our experience in prior trials, we anticipate subjects will lose 4-6% of their body weight over 5-8-weeks as a result of the weight loss intervention.

Subjects will have weekly visits with the study dietician until the time of the radical prostatectomy. [name] or her associates will oversee each of these visits with the study dietician. The subject will receive instruction on recipes, ideas and places for food shopping, education on healthy food preparation, and preparation of meal replacements. Recommended diets will

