contain 20-25% energy from fat, 15-20% from protein and 50-65% from carbohydrates largely from fruits and vegetables with some whole grains. Fiber recommendations will be a total of 25 grams/day from fruits, vegetables, legumes, and high fiber cereals.

Subjects will be counseled by [name] or her associates on performing 1 hr of exercise/day including aerobic, resistance, and flexibility activities. As an exercise incentive, subjects will be given a pedometer and exercise an log (Appendix 3) to complete and results will be reviewed with the dietitian at each visit. Subjects will be weighed at each visit and waist to hip ratio will be measured at the Screening or Baseline, Weeks 2, 4 and 9. Following the 4-9-week weight loss intervention and within 3 days prior to radical prostatectomy, weight and waist to hip ratio will again be measured, fasting serum will be collected for biomarkers, and a DEXA Scan will be performed to assess the change in body fat and lean body mass as a result of the intervention. In addition, during this week subjects will also complete a 3-day Food Diary to assess dietary and caloric intake to bring with them for their final study visit prior to surgery.

At each study visit, we will go over concomitant medications, adverse events and we will assess subjects for fatigue as well as the ability to perform their usual daily tasks (functional ability). If subjects have significant loss of strength or daily function, we will take them off protocol and have them re-evaluated in the preoperative clearance clinic at the West Los Angeles VA to make sure they can safely undergo radical prostatectomy.

Post-Prostatectomy Follow-up: Subjects in the Weight Loss Group will have scheduled visits at 3 months and 9 months post-op to assess for adverse events, and to measure body weight to determine if subjects maintain the weight loss achieved during the pre-operative intervention. If they are unable to come to the VA, this visit can take place over the phone. This will be the same for the Control subjects.

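### The primary analysis is limited to men who complete the study, which is never defined, although a man who stops the diet can still supply the primary outcome

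*Combined protocol and SAP*

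**What the plan says.** All references are to section 3 (Work Proposed) of the combined protocol and SAP.

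- **Population.** Data Analysis states: "Data analyses will be performed on randomized subjects who complete the study". No exception is made for the primary outcome, and completion is not defined.
- **Missing data.** The same paragraph adds: "No imputation of missing data is planned". No as-randomized or sensitivity analysis appears anywhere.
- **Attrition.** The Overview says "we are assuming a 15% dropout rate in the Weight Loss Group". Sample Size Determination repeats it ("To account for a post-randomization attrition rate of up to 15% in the Weight Loss Group") and arrives at 35 men for that arm. The control arm has no allowance.
- **Leaving the programme.** Under Weight Loss Intervention Group: "If subjects have significant loss of strength or daily function, we will take them off protocol". Those men are then reassessed for fitness for surgery.
- **Controls.** Of the control arm the plan says: "They will have one additional visit to the VA CRC within 3 days prior to radical prostatectomy".
- **Compliance.** Secondary Statistical Analyses expects that "the intervention will have varying effects on weight based on the amount of subject compliance with the weight loss regime".
- **Primary aim.** Under Primary Outcome Variable: "The primary objective is to compare the mean apoptotic index between the Weight Loss Group and the Control Group-No Weight Loss". The index is measured in the prostatectomy specimen.

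**The concern.** Randomization protects the comparison only if men are not removed afterwards for reasons related to arm and outcome. Here the rule removes non-completers, and the plan's own arithmetic expects them in the weight-loss arm. Removal for loss of strength or function could be related to a man's disease or general health.

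The exclusion is also avoidable. The primary outcome needs no diary, serum sample, weight or biopsy value. Every participant has elected surgery, so a man who abandons the diet can usually still be analysed in his own arm.

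Finally, an undefined population for the primary test leaves a choice that could be made after the tissue has been read. The Significance section says a positive result would lead at once to larger trials, so a spurious one would have consequences.

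**Working it through.** **1. What completion could mean.** The documents support at least five readings:
- finishing the 4-9-week programme;
- attending the visit within 3 days before surgery;
- having surgery with assessable tissue;
- attending the 3- and 9-month visits;
- finishing the PSA follow-up, described as lasting 10 years.

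These give different analysis sets. Under the second, a control who misses his visit is also a non-completer, so exclusions are not confined to one arm by rule. Partly compliant men appear to stay in, since the secondary models use actual weight loss, but the line is not drawn.

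**2. The plan's own figure.** Inputs from Sample Size Determination: 30 per arm, effect size 0.74, two-sided 0.05, t-test. The noncentrality is 0.74 / √(1/30 + 1/30) = 2.87 on 58 df, giving power 80.5%. The stated 80% reproduces. On attrition, 35 × 0.85 = 29.75, consistent with 30 evaluable. The rule is thus expected to remove about 5 of 35 weight-loss men (14%) and, as planned, no controls.

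**3. Possible bias, with no true effect.** The documents give no link between dropout and apoptosis, so the link is assumed. If the 5 lost men differ from the other 30 by a gap g (in SD), the completer mean shifts by g × 5/35. In 100,000 simulated trials per row, the 5 of 35 lowest on a variable correlated rho with the outcome were dropped:

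| rho | gap g (SD) | bias = g × 5/35 (SD) | two-sided type I error |
|---|---|---|---|
| 0 | 0 | 0 | 4.9% |
| 0.3 | 0.53 | 0.08 | 6.1% |
| 0.5 | 0.89 | 0.13 | 8.2% |
| 0.7 | 1.25 | 0.18 | 11.6% |

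If the lost men have a high index instead, the bias has the same size and the opposite sign. A separate simulation with fixed gaps of 0.5, 1.0 and 1.5 SD gave 5.9%, 8.4% and 13.0% for completers. Analysing all 35 against 30 was unbiased, with error no higher than 5%.

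Balanced losses weaken the effect. If the lowest 2 of 30 controls are also dropped, the error is 5.4%, 6.3% and 7.8% for rho 0.3, 0.5 and 0.7. With 4 of 30 it is 5.2%, 5.7% and 6.7%. In that last case the bias is only about 0.01 SD even at rho 0.7; the excess comes mostly from trimming extreme values in both arms.

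**4. Power if all men with a specimen are analysed.** Suppose the 5 non-completers keep a fraction f of the effect. With 35 v 30, the average effect is 0.74 × (30 + 5f)/35. With 2 specimens missing per arm (33 v 28, the 5 still included), it is 0.74 × (28 + 5f)/33.

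| f | 35 v 30: effect, power | 33 v 28: effect, power |
|---|---|---|
| 1 | 0.740, 83.4% | 0.740, 80.9% |
| 0.5 | 0.687, 77.6% | 0.684, 74.5% |
| 0 | 0.634, 70.9% | 0.628, 67.1% |

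Simulating the mixed distribution for f = 0 at 35 v 30 gives 69.7%, so the formula is slightly generous there.

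**The case against.** The strongest reply is that completion may simply mean having assessable tissue. Sample Size Determination speaks of an evaluable sample and of attrition, not of non-adherence. The recruitment text attaches a 4-9-week delay before surgery to the weight-loss arm, while controls proceed as scheduled, so extra losses there could be men who never reach surgery. On that reading the plan's set is close to the one proposed here. This is a fair reading, but the Overview bases the 15% on experience with the weight-loss intervention, which points at least as much to dropout from the programme. The text does not settle it.

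Second, the Rationale frames the hypothesis as men who lose weight against men who do not, so a completer analysis partly answers a different question. That supports keeping it as an additional analysis. It does not remove selection from a primary objective stated as a comparison of the two groups.

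Third, the larger error rates need strong selection and the maximum attrition, and the index is unknown to patient and clinician at the time of dropout. This stands. With only 3 of 35 lost, the error is 5.6%, 6.4% and 8.2% for rho 0.3, 0.5 and 0.7; with 2 of 35 it is 5.3%, 5.9% and 6.8%.

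The secondary regressions are no remedy. They fall under the same restriction, and the models that use actual weight loss are for the serum markers. The link from weight loss to tissue is a correlation, described under Immunostaining and Interpretation.

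**Conclusion.** The concern holds and should be resolved before any tissue is read. What is certain is on the page: a completers-only rule covering the primary test, no definition of completion, no as-randomized analysis, and a loss allowance in one arm only. The size and direction of any bias are not known. Modest selection does little harm, and type I error reaches roughly 8-12% only if all 5 expected non-completers are excluded, no controls are, and the excluded men differ by about 0.9-1.25 SD. The stated sample size is arithmetically correct for 30 evaluable men per arm; the fault is in who is analysed.

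**What to change.** Replace the population sentence with wording such as: *The primary analysis includes all randomized men with an evaluable prostatectomy specimen, analysed in the arm to which they were randomized, regardless of adherence, going off protocol or post-operative follow-up; a completer analysis is supportive.* In addition:

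- Define completer before any tissue is read.
- Report missing specimens by arm with reasons, because men with a specimen are themselves a post-randomization subset.
- State the power of this analysis over the range of retained effect and of missing specimens given above.

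The cost is SAP wording and the staining of specimens that surgery yields anyway. The real price is power if non-completers dilute the effect. Holding 80% at the 7:6 ratio would take about 70 men (38 + 32) if they keep half the effect, or 81 (44 + 37) if they keep none, assuming every man yields a specimen. The sponsor should either accept the lower power openly or revisit the target of 65. Whether specimens from men who withdraw may be used depends on consent terms that were not available for this review.
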